### **2.6.3.2 SF-36 mental component summary score**

The same analyses as SF-36 PCS score will also be performed for SF-36 MCS score, except that the BPSS in the models will be replaced by baseline SF-36 MCS score (BMSS), stratum-by-BPSS and visit-by-BPSS interactions in the analysis models will be replaced by stratum-by-BMSS and visit-by-BMSS interactions, and that the cut-off of 3.4 points for the improvement and the deterioration will be replaced by 4.6 points.

The FAS will be used for the above analyses.

### **2.6.4 Handling of missing values/censoring/discontinuations**

In the analyses described in the above sections (Section 2.6.1 to 2.6.3), death is considered the worst possible outcome and hence scheduled visits after death will be imputed to be the worst score accordingly. Other missing data is assumed to be MAR.

As in Section 2.5.3, patients who discontinue from the study treatment due to adverse events, death or lack of efficacy are defined as patients who discontinued from the study treatment during the randomized treatment epoch, and had the primary reason for discontinuation of study treatment (CRF page: “End of Study Treatment”) specified as “Adverse event”, “Death” or “Lack of efficacy”.

As sensitivity analyses, the controlled multiple imputation approach based on pattern mixture models will be applied ([Carpenter and Kenward 2013](#)), whereby all missing data of patients in the LCZ696 group who permanently discontinue study treatment due to: adverse events, death

or lack of efficacy, will be assumed to behave like patients in the IMT group after permanent discontinuation and will be imputed based on the data from patients in the IMT group according to the stratum (ACEi, ARB, No RASi).

- For changes from baseline in KCCQ CSS, for each post-baseline scheduled visit up to Week 24 (Week 4, Week 12, Week 16 and Week 24), the imputation model will be a linear regression model specified using fully conditional specifications, in which, the response variable will be the change from baseline in KCCQ CSS at the visit; region will be included as a fixed-effect factor; BCSS, BSBP, change from baseline in KCCQ CSS at the closest previous post-baseline scheduled visit (not applicable for Week 4, Week 4 for Week 12, Week 12 for Week 16, Week 16 for Week 24) will be included as covariates. For each stratum (ACEi, ARB, No RASi), the imputation model will be fitted separately based on the data from patients in the IMT group within the stratum.
- For changes from baseline in KCCQ OSS, for each post-baseline scheduled visit up to Week 24 (Week 4, Week 12, Week 16 and Week 24), the imputation model will be a linear regression model specified using fully conditional specifications, in which, the response variable will be the change from baseline in KCCQ OSS at the visit; region will be included as a fixed-effect factor; BOSS, BSBP, change from baseline in KCCQ OSS at the closest previous post-baseline scheduled visit (not applicable for Week 4, Week 4 for Week 12, Week 12 for Week 16, Week 16 for Week 24) will be included as covariates. For each stratum (ACEi, ARB, No RASi), the imputation model will be fitted separately based on the data from patients in the IMT group within the stratum.
- For NYHA class change, for each post-baseline scheduled visit up to Week 24 (Week 2, Week 4, Week 8, Week 12, Week 16, Week 20 and Week 24), the imputation model will be a proportional cumulative odds model specified using fully conditional specifications, in which, the response variable will be the NYHA class change (order defined by “improved” < “unchanged” < “worsened”) at the visit; region, baseline NYHA class, NYHA class change at the closest previous post-baseline scheduled visit (not applicable for Week 2, Week 2 for Week 4, Week 4 for Week 8, Week 8 for Week 12, Week 12 for Week 16, Week 16 for Week 20 and Week 20 for Week 24) will be included as fixed-effect factors; BSBP will be included as a covariate. For each stratum (ACEi, ARB, No RASi), the imputation model will be fitted separately based on the data from patients in the IMT group within the stratum.
- For changes from baseline in SF-36 PCS score, for each post-baseline scheduled visit up to Week 24 (Week 16 and Week 24), the imputation model will be a linear regression model specified using fully conditional specifications, in which, the response variable will be the change from baseline in SF-36 PCS score at the visit; region will be included as a fixed-effect factor; BPSS, BSBP, change from baseline in SF-36 PCS score at the closest previous post-baseline scheduled visit (not applicable for Week 16, Week 16 for Week 24) will be included as covariates. For each stratum (ACEi, ARB, No RASi), the imputation model will be fitted separately based on the data from patients in the IMT group within the stratum.
- For changes from baseline in SF-36 MCS score, for each post-baseline scheduled visit up to Week 24 (Week 16 and Week 24), the imputation model will be a linear regression model specified using fully conditional specifications, in which, the response variable will

be the change from baseline in SF-36 MCS score at the visit; region will be included as a fixed-effect factor; BMSS, BSBP, change from baseline in SF-36 MCS score at the closest previous post-baseline scheduled visit (not applicable for Week 16, Week 16 for Week 24) will be included as covariates. For each stratum (ACEi, ARB, No RASi), the imputation model will be fitted separately based on the data from patients in the IMT group within the stratum.

All other missing data will be considered as MAR within each arm and will be imputed using a multiple imputation approach ([Carpenter and Kenward 2013](#)) based on observed data within each arm according to the stratum. Of note, patients who permanently discontinue study treatment, are not considered discontinued from the study. It is planned to continue to collect and use data at scheduled visits even after permanent discontinuation of study treatment.

- For changes from baseline in KCCQ CSS, for each post-baseline scheduled visit up to Week 24 (Week 4, Week 12, Week 16 and Week 24), the imputation model will be a linear regression model specified using fully conditional specifications, in which, the response variable will be the change from baseline in KCCQ CSS at the visit; region will be included as a fixed-effect factor; BCSS, BSBP, change from baseline in KCCQ CSS at the closest previous post-baseline scheduled visit (not applicable for Week 4, Week 4 for Week 12, Week 12 for Week 16, Week 16 for Week 24) will be included as covariates. For each stratum (ACEi, ARB, No RASi) and each arm, the imputation model will be fitted separately based on the data from patients in the arm within the stratum.
- For changes from baseline in KCCQ OSS, for each post-baseline scheduled visit up to Week 24 (Week 4, Week 12, Week 16 and Week 24), the imputation model will be a linear regression model specified using fully conditional specifications, in which, the response variable will be the change from baseline in KCCQ OSS at the visit; region will be included as a fixed-effect factor; BOSS, BSBP, change from baseline in KCCQ OSS at the closest previous post-baseline scheduled visit (not applicable for Week 4, Week 4 for Week 12, Week 12 for Week 16, Week 16 for Week 24) will be included as covariates. For each stratum (ACEi, ARB, No RASi) and each arm, the imputation model will be fitted separately based on the data from patients in the arm within the stratum.
- For NYHA class change, for each post-baseline scheduled visit up to Week 24 (Week 2, Week 4, Week 8, Week 12, Week 16, Week 20 and Week 24), the imputation model will be a proportional cumulative odds model specified using fully conditional specifications, in which, the response variable will be the NYHA class change (order defined by “improved” < “unchanged” < “worsened”) at the visit; region, baseline NYHA class, NYHA class change at the closest previous post-baseline scheduled visit (not applicable for Week 2, Week 2 for Week 4, Week 4 for Week 8, Week 8 for Week 12, Week 12 for Week 16, Week 16 for Week 20 and Week 20 for Week 24) will be included as fixed-effect factors; BSBP will be included as a covariate. For each stratum (ACEi, ARB, No RASi) and each arm, the imputation model will be fitted separately based on the data from patients in the arm within the stratum.
- For changes from baseline in SF-36 PCS score, for each post-baseline scheduled visit up to Week 24 (Week 16 and Week 24), the imputation model will be a linear regression model specified using fully conditional specifications, in which, the response variable will be the change from baseline in SF-36 PCS score at the visit; region will be included as a

fixed-effect factor; BPSS, BSBP, change from baseline in SF-36 PCS score at the closest previous post-baseline scheduled visit (not applicable for Week 16, Week 16 for Week 24) will be included as covariates. For each stratum (ACEi, ARB, No RASi) and each arm, the imputation model will be fitted separately based on the data from patients in the arm within the stratum.

- For changes from baseline in SF-36 MCS score, for each post-baseline scheduled visit up to Week 24 (Week 16 and Week 24), the imputation model will be a linear regression model specified using fully conditional specifications, in which, the response variable will be the change from baseline in SF-36 MCS score at the visit; region will be included as a fixed-effect factor; BMSS, BSBP, change from baseline in SF-36 MCS score at the closest previous post-baseline scheduled visit (not applicable for Week 16, Week 16 for Week 24) will be included as covariates. For each stratum (ACEi, ARB, No RASi) and each arm, the imputation model will be fitted separately based on the data from patients in the arm within the stratum.

Furthermore, the missing data patterns in the secondary endpoint variables will be explored via by-treatment-group box plots or bar plots as appropriate for patients who permanently discontinue from study treatment due to adverse events or lack of efficacy, for patients who permanently discontinue study treatment due to any other reasons, for patients who did not permanently discontinue study treatment and for patients who take open label LCZ696 after permanent discontinuation from study treatment. Similar box plots or bar plots will also be provided for on-treatment assessments.

As additional supportive analyses, the main analyses for the secondary endpoints described in the above sections (Section 2.6.10 to 2.6.3), will be performed for the following data.

- Data where the responses after the death were set to missing for patients who died.
- Data where the LOCF approach was performed for missing data .
- Data where the responses after the first dose of open-label RASi or open-label LCZ696 after permanent discontinuation of study treatment will be set to missing and considered MAR. (This is called on-treatment analysis.)

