**2.6.1.1 KCCQ clinical summary score (CSS) change from baseline**

For patients who have died, the KCCQ CSS after the death will be imputed as zero.

For patients who permanently discontinue study treatment, values collected after permanent discontinuation will generally be included in the analysis.

The changes from baseline in KCCQ CSS will be analyzed using a MMRM model, in which, the response variable will be the changes from baseline in KCCQ CSS; stratum (ACEi, ARB, No RASi), region, treatment (LCZ696, IMT), visit and treatment-by-visit interaction will be included as fixed-effect factors; baseline KCCQ CSS (BCSS), BSBP, stratum-by-BCSS, stratum-by-BSBP, and visit-by-BCSS interactions will be included as covariates; the within-patient covariance will be modeled using an unstructured covariance matrix (a common matrix for the two treatment groups). If the model fitting procedure does not converge, the AR(1) covariance structure will be used. The analysis will include all post-baseline scheduled visits up to Week 24 (Week 4, Week 12, Week 16 and Week 24) and will be performed based on the likelihood method with an assumption of MAR for missing data (other than due to death).

Based on the MMRM model, the secondary null hypothesis,  $H_3$ , will be tested (if applicable) based on the testing strategy, the estimates and the two-sided 95% confidence intervals will be provided for the adjusted mean changes from baseline in KCCQ CSS at each post-baseline scheduled visit (Week 4, Week 12, Week 16 and Week 24) in both treatment groups (LCZ696 and IMT), and for the adjusted mean difference (LCZ696 minus IMT) at each post-baseline scheduled visit (Week 4, Week 12, Week 16 and Week 24). The corresponding one-sided p-values will also be provided based on the MMRM model.

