**Table 2-8 NYHA Class Change**

NYHA Class Change		Post-Baseline Visit				
		Class I	Class II	Class III	Class IV	Death
Baseline	Class I	unchanged	worsened	worsened	worsened	worsened
	Class II	improved	unchanged	worsened	worsened	worsened
	Class III	improved	improved	unchanged	worsened	worsened
	Class IV	improved	improved	improved	unchanged	worsened

For patients who died, the NYHA class will be set to a fifth category (death), and the NYHA class change after the death will be categorized into “worsened”. For patients who permanently discontinue study treatment, values collected after permanent discontinuation will generally be included in the analysis.

The NYHA class change will be analyzed using a longitudinal proportional cumulative odds model, in which, the response variable will be the NYHA class change (order defined by “improved” < “unchanged” < “worsened”); stratum (ACEi, ARB, No RASi), region, treatment (LCZ696, IMT), visit, treatment-by-visit interaction, baseline NYHA class, stratum-by-baseline and visit-by-baseline interactions will be included as fixed-effect factors; BSBP and stratum-by-BSBP interaction will be included as covariates; patient-specific intercepts will be included as random effects. The analysis will include all post-baseline scheduled visits up to Week 24 (Week 2, Week 4, Week 8, Week 12, Week 16, Week 20 and Week 24) and will be performed based on the likelihood method with an assumption of MAR for missing data (other than due to death).

Based on the longitudinal proportional cumulative odds model, the secondary null hypothesis, H4, will be tested based on the testing strategy (if applicable), the estimate and the two-sided 95% confidence interval will be provided for the adjusted odds ratio (LCZ696 / IMT) at each post-baseline scheduled visit (Week 2, Week 4, Week 8, Week 12, Week 16, Week 20 and Week 24). The corresponding one-sided p-values will also be provided based on the model.

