### 3 Sample size calculation

The sample size (2500 randomized patients) has been chosen in order to provide adequate power to evaluate both primary and secondary endpoints.

With an alpha of one-sided 0.0225, the power for the NT-proBNP will range from 92% to more than 99%, to detect a relative reduction ranging from 11% to 24% in change from baseline to Week 12 in NT-proBNP, assuming a standard deviation of 0.81 for change from baseline in the log-transformed NT-proBNP (based on PARAMOUNT-HF data of patients with baseline KCCQ CSS < 75) and an overall drop-out rate of 10%.

With an alpha of one-sided 0.0025, the power for the 6MWD will range from 90% to 99%, to detect a mean difference ranging from 22 meters to 30 meters in change from baseline to Week 24 in 6MWD, assuming a standard deviation of 120 meters ([Ingle et al 2005](#)), an overall drop-out rate of 10%, and an overall proportion of 88% for patients with B6MWD ranging from 100 meters to 450 meters.

With an alpha of one-sided 0.0225, the power for the KCCQ CSS will range from 87% to 99%, to detect a mean difference ranging from 2 points to 3 points in change from baseline to Week 24 in KCCQ CSS, assuming a standard deviation of 15.52 points for change from baseline in the KCCQ CSS (based on PARAMOUNT-HF data of patients with baseline KCCQ CSS < 75) and an overall drop-out rate of 5%.

All alpha levels in the following sample size calculations will be one-sided 0.025.

This sample size of 2500 randomized patients aims to provide a power of approximately 90%, with the one-sided alpha level of 0.025, to demonstrate a 5% responder advantage in at least 5-point deterioration for patients who are treated with LCZ696 over IMT when assuming the proportion of patients with at least 5-point deterioration from baseline to Week 24 in the IMT group is 20% (based on PARAMOUNT-HF data of patients with baseline KCCQ CSS < 75) and an overall 5% dropouts.

With the same assumption of the dropout rate, this sample size will also provide a power of 69% to detect a 5% responder advantage in at least 5-points improvement in the KCCQ clinical summary score for patients who are treated with LCZ696 over IMT when assuming the proportion of patients with at least 5-points improvement from baseline to Week 24 in the IMT group is 55% (based on PARAMOUNT-HF data of patients with baseline KCCQ CSS < 75).

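### The controlled imputation for KCCQ and NYHA conditions on one earlier visit only, so its result cannot be attributed to the MNAR assumption alone (minor)

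*SAP*

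**What the plan says.** SAP section 2.6.4 lists the imputation covariates visit by visit. For KCCQ CSS they are region, baseline score, baseline systolic pressure and "change from baseline in KCCQ CSS at the closest previous post-baseline scheduled visit": Week 4 for Week 12, Week 12 for Week 16, Week 16 for Week 24. KCCQ OSS follows the same pattern. For NYHA, over seven visits, the post-baseline term is "NYHA class change at the closest previous post-baseline scheduled visit". The method is labelled fully conditional specification, but no earlier post-baseline visit enters.

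The same one-visit models serve two purposes. Fitted in IMT, they impute LCZ696 patients who stopped treatment for adverse events, death or lack of efficacy. Fitted within arm, they impute all other missing data, including every missing IMT value.

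The main analyses use more history. For H3 (section 2.6.1.1), "the within-patient covariance will be modeled using an unstructured covariance matrix", with AR(1) only as a fallback on non-convergence. For H4 (section 2.6.2), "patient-specific intercepts will be included as random effects". Section 2.6.4 also plans an LOCF analysis, a run with values after death set to missing, and an on-treatment run.

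**The concern.** A sensitivity analysis for missing data is easiest to read when it changes one assumption. This one makes the intended change, which is that certain LCZ696 dropouts follow IMT. It also makes a second one: once the preceding visit is known, or has been imputed, all earlier visits are ignored. If patients differ persistently from one another, a chain of one-step imputations pulls a dropout back towards the arm mean faster than the main model would.

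H3 and H4 belong to the alpha-controlled procedure, and this is their only reference-based MNAR analysis. If LCZ696 lost more patients who were doing badly, a reassuring result could come partly from the shortened history. NT-proBNP, 6MWD and SF-36 are unaffected: each has two modelled visits, so one earlier visit is the whole history.

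**Working it through.** **Inputs from SAP section 3.** "With an alpha of one-sided 0.0225, the power for the KCCQ CSS will range from 87% to 99" percent; "to detect a mean difference ranging from 2 points to 3 points"; "assuming a standard deviation of 15.52 points for change from baseline in the KCCQ CSS"; "an overall drop-out rate of 5" percent; 2500 patients, 1:1.

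**The plan's own figure.** n per arm = 2500 × 0.95 / 2 = 1187.5. SE = 15.52 × √(2/1187.5) = 0.64. At one-sided 0.0225 the power is 87.2% for 2 points and 99.7% for 3 points, so the stated range reproduces.

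**Assumptions not in the documents.** Between-visit correlation ρ, read as conditional on the baseline covariates; a constant treatment effect d = 2; a dropout last seen at Week 4, D points below the arm mean; all LCZ696 dropouts in the group imputed from IMT.

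**One LCZ696 patient, Week 24 mean relative to the IMT mean, equal correlation:**

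- main MAR model: d − ρD
- controlled, as written (three one-visit steps): ρ³(d − D)
- controlled, full history: ρ(d − D)
- as written exceeds MAR when D > d(1 − ρ³)/(ρ − ρ³)

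| ρ | MAR, D = 10 | As written | Full history | Reversal beyond D |
|---|---|---|---|---|
| 0.5 | −3.0 | −1.0 | −4.0 | 4.67 |
| 0.6 | −4.0 | −1.73 | −4.8 | 4.08 |
| 0.7 | −5.0 | −2.74 | −5.6 | 3.68 |

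Under AR(1) the Week 4 to Week 24 correlation is itself ρ³. As written minus MAR is then −d(1 − ρ³), always negative, so no reversal occurs. In between, with half the correlation constant and half decaying (lag one 0.6, lag three 0.5 × 0.6 + 0.5 × 0.216 = 0.408), the threshold rises to 1.568/(0.408 − 0.216) = 8.2 points.

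**Treatment contrast, ρ = 0.6, dropout after Week 4, same D in both arms.** For D = 10, each LCZ696 dropout moves by −1.73 + 4.0 = +2.27. Each IMT dropout moves by −2.16 + 6.0 = +3.84, although no MNAR assumption applies to IMT. Multiplying by the loss rates:

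| Loss LCZ696 / IMT | D | LCZ696 shift | IMT shift | Net vs MAR, as written | Net, full history |
|---|---|---|---|---|---|
| 5% / 5% | 10 | +0.114 | +0.192 | −0.078 | −0.040 |
| 7.5% / 2.5% | 10 | +0.170 | +0.096 | +0.074 | −0.060 |
| 7.5% / 2.5% | 15 | +0.314 | +0.144 | +0.170 | −0.060 |

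For ρ from 0.4 to 0.8 and D of 10 or 15, the as-written net is −0.094 to −0.049 at 5%/5%, −0.045 to +0.028 at 6%/4%, and +0.028 to +0.170 at 7.5%/2.5%. If LCZ696 dropouts also decline more (15 against 5 points, ρ = 0.6), it is +0.114 at 5%/5% and +0.266 at 7.5%/2.5%.

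**LOCF in the same setting.** It keeps the whole decline. At 7.5%/2.5%, ρ = 0.6 and a flat mean profile, both arms' dropouts move by −(1 − ρ)D. The net is −0.4 × 10 × 0.05 = −0.20 for D = 10 and −0.30 for D = 15.

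**NYHA, patient level only.** I used a random-intercept cumulative logit with IMT margins 14/80/6% and LCZ696 margins 19/76/5%, leaving out baseline class. After worsening at Weeks 2, 4 and 8 and then missing, the probability of worsened at Week 24 is 0.26, 0.59, 0.74 and 0.81 under the main model for intercept SD 1, 2, 3 and 4. Under the one-visit rule it is 0.060, 0.065, 0.089 and 0.133.

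**The case against.** Several points on the other side stand.

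- LOCF is planned and is not a MAR method. In the unbalanced setting above it moves against LCZ696, so the controlled imputation is not the sole departure from MAR.
- At the single overall 5% loss assumed in SAP section 3, with equal declines, the one-visit rule is the more conservative version, and full history would relax it slightly.
- The KCCQ reversal depends on correlations that the documents do not give, and it vanishes under AR(1).
- Data after treatment discontinuation are kept, so few values need imputing.
- The SAP says only that these dropouts behave like IMT patients; it does not promise to carry forward each patient's full history.
- For NYHA, few patients are expected to worsen and models are fitted by stratum and arm, so a sparse model is defensible.

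A reader might infer that the analysis is biased towards LCZ696 for both hypotheses. The documents do not support that. The sign of the contrast depends on imbalance in loss and decline, which cannot be known in advance. The sign change in the first table concerns one patient's imputed mean, not the between-arm estimate. For NYHA only patient-level probabilities have been worked out, without baseline class.

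What survives is the attribution problem. Even the IMT arm mean moves, by 0.19 points in the 5%/5% example, for reasons unrelated to MNAR.

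**Conclusion.** The point holds as a minor one. Sections 2.6.1.1, 2.6.2 and 2.6.4 of the SAP assume different within-patient dependence, so the controlled analysis for H3 and H4 cannot isolate the effect of the MNAR assumption. On KCCQ, with equal correlation of 0.5 to 0.7 and a 2-point effect, LCZ696 patients last seen at Week 4 and more than about 4 points below the arm mean are scored better than under MAR.

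With similar declines in both arms, the contrast moves by less than 0.1 points against LCZ696 at 5% equal loss, and by roughly 0.0 to 0.2 points towards it at three-to-one loss. The latter is at most about a quarter of the 0.64 standard error (0.170/0.64 = 0.27). These sizes rest on assumed correlations and early dropout. No between-arm size is established for NYHA. The analysis decides no hypothesis test.

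**What to change.** In SAP section 2.6.4, in both the IMT-based and the within-arm imputation models, condition KCCQ CSS and KCCQ OSS on the changes at all earlier post-baseline scheduled visits (at most three covariates). For NYHA, keep the closest previous visit and add the earlier class changes, or one summary of them where cells are sparse; choose the form before unblinding.

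The cost is SAP wording, a longer covariate list in the code and a few more parameters in each stratum-by-arm model. No new data are needed and the main tests do not change.
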